## 1. OBJECTIVES

### 1.1 Primary Objectives

1.1.1 To evaluate the efficacy of Sn-117m-DTPA on sustained pain response in patients with castration-resistant prostate cancer (CRPC) metastatic to at least two bone sites with at least one clinically meaningful pain at baseline ( $\geq 4$  on an 11-point pain intensity scale). Sustained pain response is defined as: 1) achieving pain index  $\leq 3$  within a 12-week period and 2) maintaining pain index  $\leq 3$  over a 16-week period.

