## 3.2 Exclusion Criteria

- 3.2.1 Patients must not have visceral metastases (such as liver and lung) as assessed by

abdominal/pelvic CT or chest X-ray within 12 weeks before starting study treatment.

- 3.2.2 Patients must not have malignant lymphadenopathy exceeding 3 cm in short-axis diameter.
- 3.2.3 Patients must not have imminent or established spinal cord compression based on clinical findings and/or MRI.
- 3.2.4 Patients who have had chemotherapy, immunotherapy, or external radiotherapy within 4 weeks prior to entering the study.
- 3.2.5 Patients must not have received systemic radiotherapy with radium-223, strontium-89, samarium-153, rhenium-186, or rhenium-188 for the treatment of bony metastases within 24 weeks before starting study treatment.
- 3.2.6 Patients who have not recovered from adverse events due to prior anti-cancer therapy (*i.e.*, have residual toxicities > Grade 1) with the exception of alopecia.
- 3.2.7 Patients must not have received any investigational agents within 4 weeks before starting study treatment, nor be scheduled to receive one during the planned treatment period.
- 3.2.8 Patients must not have unmanageable urinary incontinence.
- 3.2.9 Patients must not have had known non-pathological bone fractures within 2 months before starting study treatment.
- 3.2.10 Patients must not have a history of allergic reactions attributed to compounds of similar chemical or biologic composition to Sn-117m-DTPA.
- 3.2.11 Patients must not have uncontrolled intercurrent illness, including:
  - Any uncontrolled infection
  - Grade 2 or greater motor or sensory neuropathy
- 3.2.12 Patients with psychiatric illness/social situations that would limit compliance with study requirements.

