#### Classification of pain index based on diary pain intensity rating and analgesic intake

Pain response	Pain index	Diary pain rating change from baseline	Analgesic intake compared with baseline
Complete	1	Decrease $\geq 90\%$	Stable or reduced
Marked	2	Decrease $\geq 50\%$ to $< 90\%$	Stable or reduced
Moderate	3	Decrease $> 33\%$ to $< 50\%$	Stable or reduced
Minimal	4	Decrease $\geq 20\%$ or increase $< 33\%$	Stable
None	5	Decrease $< 20\%$ or increase $> 33\%$	Stable

Pain progression	6	Increase $\geq 20\%$	Stable or increased
		Decrease $<20\%$ or increase $<20\%$	Increased
		Decrease $\geq 20\%$	Increased

This pain index is derived from a combination of the following 11-point pain intensity scale and analgesic consumption categorized according to the World Health Organization (WHO) analgesic ladder.

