## 6. TREATMENT PLAN

### 6.1 Agent Administration

Treatment will be administered on an outpatient basis. Reported adverse events and potential risks are described in Section 10. Appropriate dose modifications are described in Section 7. No investigational or commercial agents or therapies other than those described in Sections 6.1 and 6.3 may be administered with the intent to treat the patient's malignancy.

Study Regimen Description				
Agent	Dose	Route	Schedule	Cycle Length
Sn-117m-DTPA	20 mCi/70 kg (0.28 mCi/kg)	Slow IV injection over 10 min	Day 1	8 weeks*

\*Treatment continues for 2 cycles.

**Retreatment** after 2 cycles is allowed after an evaluation of AEs if:

- pain ( $\geq 4$  on 11-point intensity scale) recurs within 6 months after a 16-week pain observation period  
AND
- no disease progression on bone scans ( $\leq 2$  new bone lesions), or evidence of clinical progression (such as development of cancer-related symptoms)

Patients will be administered two additional cycles (8 weeks apart) if they meet the retreatment criteria. The maximum treatment dose per patient is four injections in this study.

Patients will be instructed to maintain a high fluid intake (drink at least two to three quarts of fluid every 24 hours) for 2 weeks after each Sn-117m-DTPA treatment to minimize a concentrated radioactive excretion. In general, drinking alcoholic beverages should be kept to a minimum or avoided completely. Patients will be educated on hygiene instruction/precautions on post-therapy treatment (see Appendix I).

Required Criteria for Each Re-Treatment:

Patients must have adequate organ and marrow function as defined below to be eligible for subsequent treatments after the first treatment administration:

- leukocytes	$\geq 2,000/\text{mcL}$
- absolute neutrophil count	$\geq 1,000/\text{mcL}$
- platelets	$\geq 75,000/\text{mcL}$
- hemoglobin	$\geq 8.0 \text{ g/dL}$
- total bilirubin	$\leq 2.5 \times \text{institutional ULN}$
- AST(SGOT)/ALT(SGPT)	$\leq 5 \times \text{institutional ULN}$
- creatinine*	$\leq 1.7 \text{ mg/dL}$
	OR
- glomerular filtration rate (GFR)	$\geq 50 \text{ mL/min}/1.73 \text{ m}^2$ (see Appendix B)

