## 6.3 General Concomitant Medication and Supportive Care Guidelines

### 6.3.1 Concomitant Prostate Cancer Therapy

- Patients receiving bisphosphonates or denosumab prior to enrollment can maintain therapy throughout all or part of the study. The bisphosphonate may be stopped or

started at the discretion of the investigator throughout the study (*i.e.*, both treatment phase and follow-up). Injection of bisphosphonates should be done at least 2 hours before or after study drug administration.

- Patients who have not undergone bilateral orchiectomy are allowed and should receive LHRH agonists or antiandrogen such as bicalutamide throughout the study (*i.e.*, both treatment phase and follow-up).
- Cytotoxic chemotherapy, androgen receptor blockers, androgen biosynthesis inhibitors, other systemic radioisotopes, hemi-body external radiotherapy, and other investigational drugs should not be used during the treatment period. These treatments can be given if at least 8 weeks after the last injection.
- Colony stimulating factors (*e.g.*, erythropoietin and granulocyte colony stimulating factors) and transfusions products (*e.g.*, red blood cell transfusion, and/or platelet transfusion) as dictated by standard practice are acceptable while the subject is enrolled in the study.

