## 7. DOSING DELAYS/DOSE MODIFICATIONS

No Sn-117m-DTPA dose modification is allowed. Patients will be monitored continuously for AEs throughout the study. Patients must be instructed to notify their physician immediately for any and all side effects. Treatment interval is scheduled every 8 weeks or every 56 days with a window period of +/- 7 days for all time points. If the treatment needs to be delayed due to an adverse event, study drug administration can be delayed up to 8 weeks for recovery, with the following conditions:

- Hematological toxicities must resolve to CTCAE grade 1 or less (or, if abnormal at baseline, not more than one grade above baseline) prior to administration of the next Sn-117m-DTPA dose. In the absence of recovery after 4 weeks, patients are to discontinue further study drug administrations.
- Non-hematological toxicities must resolve to CTCAE grade 2 (gastrointestinal events) or grade 3 (other toxicities) prior to administration of the next dose.
- If patients experience spinal cord compression during the treatment phase, Sn-117m-DTPA administration can continue with up to a 4-week delay if the patient is adequately treated with steroids, local SBRT, or surgery.
- If patients experience traumatic fracture in weight-bearing bones during the treatment phase, the study drug administration should be delayed 4 weeks from the fracture.

As a general approach, it is suggested that all AEs be managed with supportive care when possible at the earliest signs of toxicity.

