### 9. STATISTICAL CONSIDERATIONS

#### 9.1 Study Design/Endpoints

This is a single-arm, open-label phase 2 study to evaluate the efficacy of Sn-117m-DTPA on

sustained pain response in patients with CRPC metastatic to at least two bone sites, with at least one clinically meaningful pain at baseline ( $\geq 4$  on an 11-point pain intensity scale). Sustained pain-response is defined as: 1) achieving pain index  $\leq 3$  within a 12-week period and 2) maintaining that pain index  $\leq 3$  over a 16-week time period (beginning when the pain index  $\leq 3$  is initially achieved). The maximum duration of follow-up required to declare a patient a responder is 28 weeks, representing a patient who initially achieves pain index  $\leq 3$  toward the end of the 12-week period and is followed for an additional 16 weeks to confirm maintenance of pain index  $\leq 3$ .

Eligible patients will be assigned to receive Sn-117m-DTPA at 20 mCi/70 kg (0.28 mCi/kg) every 8 weeks for two cycles. Treatment will last for 16 weeks with two treatment injections given at 8-week intervals. The study utilizes a mini-max Simon two-stage design to assess anti-tumor activity and pain benefit of Sn-117m-DTPA.

Patients are not allowed to receive external radiation within 12 weeks from the start of treatment administration. If their pain index does not reach  $\leq 3$  after 12 weeks, they are not meeting the primary endpoint, and they can then get external radiation for pain control.

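### The sustained-response endpoint has no scoring rule for local radiation or surgery given before the 16-week maintenance window ends

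*Combined protocol and SAP*

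**What the plan says.** **Endpoint.** Sections 1.1.1 and 9.1 require a pain index of 3 or less within 12 weeks, then maintenance for 16 weeks from the first such score. The table in Section 5.10.2.2.1, "Classification of pain index based on diary pain intensity rating and analgesic intake", builds the index from the worst-pain rating and analgesic intake and from nothing else.

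**Radiation.** Section 9.1: "Patients are not allowed to receive external radiation within 12 weeks from the start of treatment administration". For a patient who has not reached 3 or less by then, it adds that "they are not meeting the primary endpoint, and they can then get external radiation for pain control". Section 6.3.1 says that "hemi-body external radiotherapy, and other investigational drugs should not be used during the treatment period", and releases the treatments on its list 8 weeks after the last injection. Local-field radiation and surgery are not on that list.

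**Cord compression.** Section 3.2 excludes it at entry: "Patients must not have imminent or established spinal cord compression based on clinical findings and/or MRI". If it occurs during the treatment phase, Section 7 says "Sn-117m-DTPA administration can continue with up to a 4-week delay if the patient is adequately treated with steroids, local SBRT, or surgery".

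**Other restrictions.** Section 6.1 limits other therapies given with intent to treat the malignancy to those described in Sections 6.1 and 6.3. Section 9.6.2 removes patients with major violations that could affect efficacy assessment, whereas Section 9.1 keeps every dosed patient in the denominator of the response rate. Neither section mentions local radiation or surgery.

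**The concern.** Local radiation or surgery can relieve the same pain that the index scores. After such treatment the index still returns a value, and nothing tells the analyst to set it aside. Two routes lead to a wrong credit.

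- **Route (a).** Cord compression occurs between injections 1 and 2 and is treated with SBRT or surgery, and the relief brings the index to 3 or less by Week 12.
- **Route (b).** A patient already at 3 or less receives EBRT or SBRT after Week 12, or surgery at any time, within his 16-week window, and the local treatment keeps the index down.

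The trial is single-arm, is tested against a fixed 10% null that Section 9.1 ties to the absence of effective therapy, and succeeds at 6 responders of 25. A wrong credit can only raise the count. Sites also receive conflicting instructions: Section 7 accepts SBRT at a time when Section 9.1 bars external radiation and states no exception.

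**Working it through.** **1. Timeline.** If the index first reaches 3 or less at Week t, the window ends at Week t + 16. The ban ends at Week 12, so (t + 16) − 12 weeks are uncovered. For t = 2 this is 6 weeks (window ends Week 18); for t = 12 it is 16 weeks (window ends Week 28). Injection 2 falls at Week 8, or Week 12 with the 4-week delay, so SBRT given before it normally lies inside the ban. With injection 2 at Week 8, the release in Section 6.3.1 comes at about Week 16, before even the earliest window closes.

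**2. The plan's own figures.** Success requires at least 2 responders in stage 1 and at least 6 of 25 in total. Exact binomial: P(success) = Σ over x ≥ 2 of P(X1 = x) × P(X2 ≥ 6 − x).

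| Stages | Type I error (p = 0.10) | Power (p = 0.30) | Stop early under the null |
|---|---|---|---|
| 15 then 10 | 3.28% | 80.17% | 54.9% |
| 10 then 15 (printed) | 2.77% | 74.0% | 73.6% |

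The quoted 3.28%, 80.17% and about 55% match only 15 then 10. That is a separate matter; both versions are carried below, 15+10 first.

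**3. False-positive risk.** The documents give no rates, so every event input is assumed. It is also assumed that the 10% null excludes relief from local treatment and that Section 9.6.2 removes nobody.

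- Route (a): counted rate = 0.10 + c × 0.9 × s, where c is the share of patients with compression treated in this way (1%–2%) and s is the share who then sustain the response (30%–50%).
- Route (b): counted rate = 0.10 + f × g × s, where f is the share who reach 3 or less but would not hold it (10%–20%), g is the share of these treated before scoring 4 or more (5%–10%), and s is as above.

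| Case | Counted rate | Risk, 15+10 | Risk, 10+15 |
|---|---|---|---|
| None | 0.1000 | 3.28% | 2.77% |
| (a) low: 0.01 × 0.9 × 0.3 | 0.1027 | 3.68% | 3.11% |
| (a) high: 0.02 × 0.9 × 0.5 | 0.1090 | 4.72% | 4.00% |
| (b) low: 0.10 × 0.05 × 0.3 | 0.1015 | 3.50% | 2.95% |
| (b) high: 0.20 × 0.10 × 0.5 | 0.1100 | 4.90% | 4.15% |
| Both, midpoint: 0.0054 + 0.0045 | 0.1099 | 4.89% | 4.14% |
| Both, high: 0.009 + 0.010 | 0.1190 | 6.74% | 5.73% |

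Expected false responders per 25 are 25 × 0.0099 = 0.25 at the midpoint and 25 × 0.019 = 0.475 at the upper end. The risk reaches 5% at a counted rate of 11.05% (15+10) or 11.51% (10+15).

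**4. How often one patient could decide.** The probability of passing stage 1 and ending at exactly 5 of 25 is 6.0% or 4.4% at a true rate of 10%, 18.3% or 13.5% at 20%, and 9.6% or 7.1% at 30%.

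**The case against.** **Section 6.1 may already bar the treatment.** Local EBRT and SBRT are described in neither Section 6.1 nor Section 6.3. But the limit covers therapy intended to treat the malignancy, which may or may not reach palliative radiation or surgery, and it gives no scoring rule.

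**Route (b) rests on silence.** A reader might infer that Section 9.1 permits responders to be irradiated after Week 12. It does not say so: the express permission goes only to patients who have already failed, and the natural reading is that radiation follows failure. What stands is narrower. For a responder, the text neither names local radiation as barred after Week 12 nor says how to score it.

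**Section 9.6.2 may remove breaches of the ban.** If it does, only the surgical part of route (a) remains. Route (b) alone peaks at 4.90% or 4.15%. This lowers the risk, but removal is not a scored failure, and the any-dose denominator in Section 9.1 leaves the handling unsettled.

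**The relief assumption is generous.** The assumed 30%–50% is at or above the plan's 30% target for the drug itself. With all other inputs at their maximum, 20% gives a counted rate of 10.76% and a risk of 4.5% or 3.8%; 30% gives 11.14% and 5.2% or 4.4%.

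**Most flares will be caught.** Scoring is every two weeks, coordinators check pain medication at clinic visits, and increased analgesic intake gives index 6. Pain severe enough for radiation or surgery will often produce a score of 4 or more first. This holds, and it is why the number affected should be small. It does not cover treatment between assessments or while the index is still 3 or less.

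**Keeping the observed score whatever local treatment is given is a legitimate choice.** It is, but the plan does not state that it has made it.

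**Conclusion.** The gap is real on the text, and it is minor. Followed literally, the endpoint can count as a sustained responder a patient whose relief came from local radiation or surgery, and no section scores him as a failure. Sections 9.1 and 7 also conflict on SBRT for cord compression before Week 12.

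A reader might infer that the trial's error control fails. The documents do not support that. They give no event rates. Under the assumed ones, each route alone and both at midpoint stay below 5%; only the upper end of both together passes it, and the excess shrinks if Section 9.6.2 removes breaches. Nor are the exactly-5-of-25 probabilities error rates: a misclassified patient must also occur, and at a true rate of 30% moving from 5 to 6 is no harm.

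A reader might also extend route (a) to cord compression during retreatment (injections 3 and 4). Retreatment follows the pain observation period, so it does not bear on the primary endpoint.

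Confidence is medium: the reading of the text is firm, the size is not.

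**What to change.** State in Sections 1.1.1 and 9.1 that a patient who receives EBRT, SBRT or orthopedic or spinal surgery to a painful bone site between dose 1 and the end of his 16-week maintenance window stays in the denominator and is a non-responder. Report the number affected and a sensitivity count that ignores the rule. Cross-reference Sections 9.1 and 7 so that SBRT for cord compression before Week 12 is either a stated exception to the ban or not allowed; the sponsor chooses which.

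**Cost.** One sentence and one cross-reference. EBRT, cord compression and orthopedic surgery are already components of the skeletal-event endpoint, but their dates must also be kept after a first event.

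**Downside.** Worst pain is one rating for the whole patient, so a true responder treated at a single site becomes a failure. If 2%–5% of true responders are affected (assumption), the 30% rate becomes 0.30 × 0.98 = 0.294 to 0.30 × 0.95 = 0.285. Power falls from 80.2% to between 78.3% and 75.4% (15+10), or from 74.0% to between 72.1% and 69.0% (10+15), about 2 to 5 points. The sensitivity count shows this effect.

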The sustained pain response rate under null hypothesis is  $p_0=0.1$  and the alternative hypothesis is  $p_1=0.3$ . The literature on sustained pain-relieving benefit with radiopharmaceutical drugs in prostate cancer with bone metastases is limited. Nilsson *et al.* studied the dose-response relationship and pain-relieving effect of radium-223 (Nilsson *et al.*, 2012). Pain response at Week 8 was seen in 40% of patients. The null hypothesis for sustained pain response in the absence of effective therapy and a strong literature support would assume 10%. We propose that the sustained pain response with Sn-117mDTPA would achieve 30%. Using the mini-max Simon's two-stage design, the total sample size is 25 patients, with 10 patients for the first stage and 15 patients for the second stage. If 1 or 0 patients achieve sustained pain response in the first stage, the study will be stopped early for futility; otherwise the trial continues to the second stage. If 5 or fewer patients achieve sustained pain-response, then no further investigation of the study treatment is warranted. This design has an estimated 5% type I error rate and 80% power. The planned sample size and interim analysis has a 3.28% actual type I error rate and 80.17% actual power. The probability of stopping at the end of the first stage is about 55% under the null hypothesis. Study enrollment will be interrupted for the interim efficacy analysis.

The efficacy primary endpoint will also be summarized by the point estimation of the ORR with the corresponding 95% confidence intervals. Patients who received any amount of study drug will be included in the denominator for the calculation of ORR.

Summary statistics on safety endpoints will be calculated and reviewed at the interim analysis or anytime during the study at the investigator's discretion. If there is statistically significant evidence that the DLT probability exceeds 30%, the study should be suspended for further review. A 95% exact binomial confidence interval will be calculated for the DLT rate. If the observed lower bound of the confidence interval exceeds 30%, we consider it statistically significant evidence that the DLT probability exceeds 30%.

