## 9.2 Sample Size/Accrual Rate

The total sample size is 25 patients, with 10 patients for the first stage and 15 patients for the second stage. An interim analysis for efficacy will be conducted after the first 10 patients have become evaluable for the primary endpoints. Study enrollment will be interrupted for the interim analysis. Patients will be accrued at an anticipated rate of 1-2 patients per month.

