## Stopping Criteria

Stopping criteria will be applied if 1) there is evidence of treatment related AEs or 2) lack of efficacy.

- 1) We will review safety data at interim analysis or at any point if there are reasons for concern about safety. If there is strong evidence that the DLT rate is unacceptably high (>30%), we will suspend the study.
- 2) An interim analysis for efficacy will be conducted after the first 10 patients have become evaluable. If 1 or 0 patients achieve the primary endpoint, then the study will be stopped early for futility.

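### The Simon design as written (10 then 15 patients) has 74.0% power; the stated 3.28%, 80.17% and 55% are those of 15 then 10

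*Combined protocol and SAP*

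**What the plan says.** Section 9.1 sets the null sustained pain response rate at 0.10 and the alternative at 0.30, names the minimax form of Simon's design, and gives the sizes: "the total sample size is 25 patients, with 10 patients for the first stage and 15 patients for the second stage". The trial stops for futility if 0 or 1 first-stage patients respond. The treatment is not pursued if 5 or fewer respond overall. Nominal type I error is 5% and nominal power 80%.

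The same paragraph then gives exact properties: "The planned sample size and interim analysis has a 3.28% actual type I error rate and 80.17% actual power". It adds: "The probability of stopping at the end of the first stage is about 55% under the null hypothesis".

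Section 9.2 repeats the 10 and 15 split and times the look: "An interim analysis for efficacy will be conducted after the first 10 patients have become evaluable for the primary endpoints". The Stopping Criteria that follow agree on timing: "An interim analysis for efficacy will be conducted after the first 10 patients have become evaluable". The documents nowhere give a first stage of 15.

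**The concern.** The early-stopping figure is the quickest sign of trouble. With 10 patients and a 10% response rate, seeing 0 or 1 responders is much more likely than 55%. If that figure is wrong for the written design, the type I error and power beside it are probably wrong too.

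This is the primary decision rule. Enrolment is paused for the look, and the count of responders decides whether the trial goes on. Because the 10-patient look appears consistently in 9.1, 9.2 and the Stopping Criteria, anyone following the text would run 10 then 15. If that rule lacks the stated power, an agent that works at the target rate is more likely to be dropped than the protocol tells its readers.

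**Working it through.** **Inputs (all from section 9.1).** Null rate p0 = 0.10; alternative p1 = 0.30; total n = 25; stage 1 boundary r1 = 1 (stop at 0 or 1); final boundary r = 5 (positive at 6 or more). Written stage sizes: n1 = 10, n2 = 15.

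**Formulas.** With X1 ~ Bin(n1, p) and X2 ~ Bin(n2, p), independent:

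- Early stopping: PET(p) = P(X1 ≤ 1).
- Positive result: R(p) = Σ over x ≥ 2 of P(X1 = x) × P(X2 ≥ 6 − x), where the second factor is 1 once x ≥ 6. Type I error is R(0.10); power is R(0.30).

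**Step 1: try to reproduce the stated figures with 10 then 15.**

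PET(0.10) = 0.9^10 + 10 × 0.1 × 0.9^9 = 0.3487 + 0.3874 = 0.7361. The plan says about 55%.

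Type I error, term by term:

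| x in stage 1 | P(X1 = x) | P(X2 ≥ 6 − x) | product |
|---|---|---|---|
| 2 | 0.19371 | 0.05556 | 0.01076 |
| 3 | 0.05740 | 0.18406 | 0.01056 |
| 4 | 0.01116 | 0.45096 | 0.00503 |
| 5 | 0.00149 | 0.79411 | 0.00118 |
| 6 or more | 0.00015 | 1 | 0.00015 |

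Sum = 0.0277. The plan says 3.28%.

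Power: the same terms at p = 0.30 are 0.16416 + 0.23299 + 0.19306 + 0.10243 + 0.04735 = 0.7400. The plan says 80.17%.

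PET(0.30) = 0.0282 + 0.1211 = 0.1493.

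None of the three stated figures is reproduced.

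**Step 2: same boundaries, 15 then 10.**

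PET(0.10) = 0.2059 + 0.3432 = 0.5490.

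Type I error = 0.00341 + 0.00902 + 0.01130 + 0.00682 + 0.00225 = 0.0328.

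Power = 0.03208 + 0.10495 + 0.18598 + 0.20031 + 0.27838 = 0.8017.

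PET(0.30) = 0.0047 + 0.0305 = 0.0353.

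All three stated figures are matched.

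**Step 3: could another design explain them?** With n = 25 and r = 5 held, n1 was run from 1 to 24 and r1 from 0 to 4. Only n1 = 15 with r1 = 1 gives 3.28% and 80.17% to the printed precision. Changing the final boundary to r = 4 with 10 then 15 gives 7.20% and 81.1%. A single-stage rule of 6 or more of 25 gives 3.34% and 80.7%.

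**Step 4: which design is minimax?** A search over two-stage designs with type I error ≤ 5% and power ≥ 80% finds none with fewer than 25 patients. Among those with 25, the rule 1/15 then 5/25 has the smallest expected size under the null, 19.5, so it is the minimax design. The optimal design, with the smallest expected size overall, is 1/10 then 5/29. The written rule, 1/10 then 5/25, is neither.

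**Comparison**

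| | Stated | 1/10, 5/25 (written) | 1/15, 5/25 |
|---|---|---|---|
| Type I error | 3.28% | 2.77% | 3.28% |
| Power | 80.17% | 74.0% | 80.17% |
| Early stop, p = 0.10 | about 55% | 73.6% | 54.9% |
| Early stop, p = 0.30 | not given | 14.9% | 3.5% |
| Expected size, p = 0.10 | not given | 14.0 | 19.5 |

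Power shortfall: 80.17 − 74.00 = 6.2 points. Ratio of false futility stops: 14.93 / 3.53 = 4.2. Difference: 11.4 points.

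**The case against.** The documents show a mismatch, not its cause. A 10-patient first stage appears wherever the look is mentioned, so the sponsor may have wanted an early look at 10 and carried over figures from a different design. An early look has merits: it stops an ineffective agent more often (73.6% against 54.9%) and with fewer patients on average. The error is also conservative for false positives, since 2.77% is below the 5% target.

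Part of this stands. The swap is an inference, though a strong one, because 15 then 10 is the minimax design that 9.1 names and the only split with these boundaries that gives the printed figures. The choice between the two designs belongs to the sponsor. The objection does not rescue the text, however: if a look at 10 is intended, the stated power and early-stopping probability are wrong, and the 80% target in the same paragraph is missed.

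**Conclusion.** The concern holds. The stage sizes and the operating characteristics in section 9.1 cannot both be right. Run as written, the trial has 74.0% power instead of 80.17%, so the false-negative risk at a 30% response rate is 26.0% instead of 19.8%. More than half of the written rule's false negatives come from the early look itself, which stops an agent with a 30% response rate 14.9% of the time. Type I error remains controlled.

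The result is exact and uses only inputs printed in 9.1. It assumes independent responses with a common rate, exactly 10 (or 15) evaluable patients at the look and 25 at the end, and boundaries applied as stated. This should be corrected before the interim analysis.

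**What to change.** **Main change.** In 9.1 and 9.2, give 15 patients to the first stage and 10 to the second. In 9.2 and the Stopping Criteria, place the interim after 15 evaluable patients. Keep both boundaries: stop at 0 or 1 of 15, negative at 5 or fewer of 25. The printed 3.28%, 80.17% and 55% are then correct and the total stays at 25.

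**If a look at 10 is wanted**, choose one of these and state its properties:

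- Keep 1/10, 5/25 and report 2.77% type I error, 74.0% power and 73.6% early stopping under the null.
- Use 0/10, 5/25: 3.26%, 79.9% and 34.9%. Power falls just short of 80%.
- Use 1/10, 5/29: 4.71%, 80.5% and 73.6%. This needs four more patients and is the optimal design, so the minimax label would go.

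**Cost of the main change.** The edit itself is a few lines. The look comes five patients later, which at the planned 1 to 2 patients per month is 5/2 = 2.5 to 5/1 = 5 months of further accrual. Expected size under the null rises from 14.0 to 19.5, if enrolment is held at the end of stage 1 until responses are known. Responses can take up to 28 weeks, and the protocol does not say exactly when the pause begins, so this should be stated in the same edit. Sections 9.1 and 9.2 also tie the only scheduled safety review to the interim, so moving the look delays that review. The sponsor should decide whether to keep a separate safety review at 10 patients.

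### The primary-endpoint estimate and 95% interval are not tied to the two-stage design: at 6/25 an exact 95% interval contains the 10% null although the rule declares success, and the raw proportion is biased

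*Combined protocol and SAP*

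**What the plan says.** Section 9.1 tests a null sustained pain response rate of 10% against 30% with a minimax Simon design: "the total sample size is 25 patients, with 10 patients for the first stage and 15 patients for the second stage". The stage 1 rule is "If 1 or 0 patients achieve sustained pain response in the first stage, the study will be stopped early for futility". The final rule is "If 5 or fewer patients achieve sustained pain-response, then no further investigation of the study treatment is warranted", so success means at least 6 of 25. On error rates the section says "This design has an estimated 5% type I error rate and 80% power" and then "The planned sample size and interim analysis has a 3.28% actual type I error rate and 80.17% actual power", with about a 55% chance of stopping at stage 1 under the null. It does not say whether the 5% is one-sided or two-sided.

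On reporting, Section 9.1 says only "The efficacy primary endpoint will also be summarized by the point estimation of the ORR with the corresponding 95% confidence intervals". It names no estimator, no interval method and no adjustment for the interim stop, and it does not define ORR for a pain endpoint. For the DLT rate, the same section does name an exact binomial 95% interval. The only method named for a response-rate interval is in Section 9.4.2, under the secondary endpoints: an exact 95% interval, attributed to Fisher, which is a single-stage method.

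**The concern.** A Simon rule rejects only for high counts, so its type I error lies wholly in the upper tail. A two-sided 95% interval gives 2.5% to each tail. If the rule's actual error exceeds 2.5%, the smallest successful count can come with an exact interval that still includes the null. A report would then say that the treatment merits further study beside an interval that does not exclude 10%.

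A separate matter is the estimate. A futility stop ends low-scoring trials early on few patients and lets the others continue, so responders divided by patients is not an unbiased estimate of the response rate. This estimate is likely to inform the planning of any later trial. Because the plan is silent, the estimator and interval method could be chosen after the count is known, and at 6/25 that choice decides whether the interval contains 10%.

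**Working it through.** **Inputs (Section 9.1).** p0 = 0.10; p1 = 0.30; stage 1 size n1 = 10; stage 2 size n2 = 15; N = 25; stop if X1 ≤ 1; success if the total S ≥ 6.

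**1. The plan's own figures.** Early stopping = P(X1 ≤ 1). Success = Σ over x ≥ 2 of P(X1 = x) × P(X2 ≥ 6 − x).

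For 10 then 15 at p = 0.10, with terms for x = 2, 3, 4, 5 and ≥6:
0.1937×0.0556 + 0.0574×0.1841 + 0.0112×0.4510 + 0.0015×0.7941 + 0.0001 = 0.0277.

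| Stages | Type I error | Power at 30% | Early stop at 10% |
|---|---|---|---|
| Stated | 3.28% | 80.17% | about 55% |
| 10 then 15 | 2.77% | 74.0% | 73.6% |
| 15 then 10 | 3.28% | 80.17% | 54.9% |

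The stated figures do not reproduce for the stage sizes as written. They match 15 then 10 with the same boundaries, so both versions are carried below.

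**2. Interval at the minimum success count, 6/25.** Both actual error rates lie above 2.5% and below 5%.

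| Interval at 6/25 | Limits | Contains 10%? |
|---|---|---|
| Exact (Clopper-Pearson) 95% | 9.4% to 45.1% | yes |
| Wald 95% | 7.3% to 40.7% | yes |
| Wilson 95% | 11.5% to 43.4% | no |
| Jeffreys 95% | 10.7% to 42.9% | no |
| Stage-wise 95%, 10 then 15 | 9.8% to 47.8% | yes |
| Stage-wise 95%, 15 then 10 | 9.4% to 45.2% | yes |
| Exact 90% | 11.0% to 42.0% | no |
| Stage-wise 90%, 10 then 15 | 11.5% to 44.1% | no |
| Stage-wise 90%, 15 then 10 | 11.1% to 42.0% | no |

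The stage-wise limits solve P(continue and S ≥ 6; p) = a for the lower limit and 1 − P(continue and S ≥ 7; p) = a for the upper, with a = 0.025 or 0.05. At p = 0.10 the first of these is the design-based p-value: 0.0277 (10 then 15) or 0.0328 (15 then 10). What removes the overlap is moving from 95% to 90%; allowing for the two stages does not.

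The stage-wise 90% interval also agrees with the rule one count lower. At 5/25 its lower limit is 9.0% (10 then 15) or 8.4% (15 then 10), both below 10%.

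**3. How often it matters.** At 7/25 the exact 95% lower limit is 12.1%, so only 6/25 is affected. The probability of continuing and ending at exactly 6:
- 10 then 15: 13.1% at a true 20%, 11.8% at a true 30%.
- 15 then 10: 16.0% at a true 20%, 14.4% at a true 30%.

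At a true 30%, that is 0.118/0.740 = 16% of successes (10 then 15) or 0.144/0.802 = 18% (15 then 10).

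**4. Bias of the raw proportion.** Sum (responders ÷ patients treated) × probability over all outcomes. For the last column, sum over outcomes with S ≥ 6 and divide by the success probability.

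| Stages | True rate | Mean, all outcomes | Mean given success |
|---|---|---|---|
| 10 then 15 | 10% | 7.9% | 25.6% |
| 10 then 15 | 20% | 17.1% | 28.5% |
| 10 then 15 | 30% | 28.0% | 33.5% |
| 15 then 10 | 10% | 8.7% | 25.5% |
| 15 then 10 | 20% | 19.0% | 28.2% |
| 15 then 10 | 30% | 29.7% | 33.1% |

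Over true rates of 10% to 40%, the largest average downward bias is 2.9 points (10 then 15) or 1.3 points (15 then 10).

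The uniformly minimum variance unbiased estimate (UMVUE) at S = 6 is Σ C(n1−1, x−1)C(n2, 6−x) ÷ Σ C(n1, x)C(n2, 6−x), for x = 2 to 6:
- 10 then 15: 39501/142065 = 27.8%.
- 15 then 10: 42252/173110 = 24.4%.

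The raw proportion is 24.0%.

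**5. Coverage of the unadjusted exact 95% interval.** Sum the probabilities of all two-stage outcomes whose interval contains the true rate. At true rates of 10%, 20% and 30% coverage is 99.2%, 98.3% and 98.1% (10 then 15), or 99.1%, 98.3% and 97.5% (15 then 10). On a half-point grid from 10% to 40% it never falls below 95.2% in either version.

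**The case against.** The strongest reply is that the decision is made on the count and the interval only describes the result. Section 9.1 gives the interval no role in the efficacy decision, whereas it expressly ties the DLT suspension rule to a confidence bound. Two-sided 95% intervals beside one-sided rules are common, and the exact interval keeps its coverage here. All of that stands, and it makes this a reporting matter.

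Three stronger readings are tempting, and the documents do not support them:

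- **That ignoring the two stages causes the overlap with 10%.** It does not: the stage-wise 95% interval at 6/25 also contains 10%. The cause is the confidence level, and even then it depends on the method, since Wilson and Jeffreys 95% intervals exclude 10%.
- **That a trial declaring success reports an estimate biased low.** The downward bias is an average that includes futility stops. Among successes the raw proportion is biased high (mean 33.5% at a true 30%, 10 then 15). That the UMVUE at 6/25 exceeds 24.0% does not change this.
- **That the plan commits to a single-stage analysis of the primary endpoint.** It is silent. The single-stage method in Section 9.4.2 is for a secondary endpoint and is only a pointer to what might be used.

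It can also be said that choosing the UMVUE is a preference. That is fair: the median-unbiased estimate at 6/25 is 23.7% (10 then 15) or 22.5% (15 then 10) and is also defensible. What matters is that one is named in advance.

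**Conclusion.** The point holds as two separate reporting gaps.

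(1) With an exact 95% interval, the reported limits contain 10% at the smallest successful count. This is confined to 6/25, with probability 11.8% (10 then 15) or 14.4% (15 then 10) at a true rate of 30%. A 90% interval removes it.

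(2) No estimator is named, and the raw proportion is biased in a direction that depends on whether one averages over all trials or only successful ones. At 6/25 the gap from the UMVUE is 3.8 points for the stage sizes as written, but only 0.4 points for the sizes that match the stated error rates.

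The go/no-go rule and its type I error are not affected, and no undercoverage was found. These results assume exactly 25 patients in the analysis, the stated boundaries followed without deviation, and the 5% read as one-sided, which a Simon rule implies but the plan does not write. The worth of the change lies in settling the method before the data are seen.

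**What to change.** First reconcile the stage sizes in Sections 9.1 and 9.2 with the stated 3.28%, 80.17% and 55%, because every design-based estimate depends on n1. At the same time settle the denominator: Section 9.1 counts everyone who received any study drug, while Section 9.6.2 uses the Per Protocol Population.

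Then state in Section 9.1 that:
- the 5% error rate is one-sided;
- the sustained pain response rate (replacing the term ORR) will be reported with a named two-stage estimate, for example the UMVUE;
- it will be accompanied by the design-based p-value and a two-sided 90% interval by stage-wise ordering, which matches the one-sided 5% rule;
- the raw proportion and its exact 95% interval will be given as descriptive figures.

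The cost is a few sentences in the plan, a few lines of code and an estimate that readers may find less familiar. For this reporting change alone, sample size, data collection and patient management stay as they are; reconciling the stage sizes is a design matter that has to be settled in any case.
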